7.0 Statistical Considerations

Primary outcome: VAS score at 24 and 48 hours

Primary Research Hypothesis: Thoracic epidural and Ultrasound guided paravertebral block with continuous catheter will provide lower pain scores compared to single shot paravertebral block.

Secondary outcomes: Opioid usage after 1, 24, 48 and 72 hours. Pain scores using VAS at rest and on movement at 1, 24, 48 and 72 hours. Patient satisfaction scores at 24 and 48 hours. Nausea scores at 1, 24, 48 and 72 hours. Sedation scores at 1, 24, 48 and 72 hours. Time to first bowel movement, incidence of urinary retention, and incidence of respiratory depression will be recorded as well.

Secondary Research Hypotheses: Thoracic epidural anesthesia and Ultrasound guided paravertebral catheter will show improved pain control, improved patient satisfaction scores, and decreased nausea and sedation scores compared to single shot paravertebral.

Statistical analysis will be performed using a standard statistical program (SAS or SPSS). All data will be summarized (means, standard deviations, standard errors, and ranges for continuous variables; frequencies and percentages for categorical variables) by group. Demographic data will be compared between the four groups using ANOVA or chi-square tests as appropriate. The primary outcome, VAS at 24 and 48 hours, will be compared between the groups using repeated measures ANOVA; the model will include fixed effects for group, time, and the group by time interaction and random effects to allow correlations between the two times and different variances for the two times. Pain and satisfaction scores and opioid usage over time will be analyzed using repeated measures ANOVA. Nausea and sedation scores will be compared between groups at each time point using Mantel-Haenszel chi-square tests for ordered categorical data. Distributions of the continuous variables will be examined, and a transformation of the data (e.g. natural logarithm) or nonparametric tests will be used as necessary. A 5% significance level will be used for all comparisons.

Based on prior studies, the coefficient of variation for the VAS score at 24 and 48 hours is estimated to be 0.70. With a sample size of 40 per group the study will be able to detect a 60% decrease in VAS score between any two groups, assuming two-sided tests each conducted at a 5% significance level.

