3.0 Enrollment/Randomization

All VATS cases scheduled by thoracic surgeons at IU Health University Hospital will be identified. The subjects will be contacted face-to-face prior to surgery. They will be informed about the study and all questions will be answered. The potential subjects will be given a copy of the informed consent form and authorization form. The subjects will then be contacted face-to-face in POCU on the day of surgery and if participation is agreed, written consent will be taken.

A total of 120 subjects will be randomized by a computer program into three groups (40 per group):

1. US- Guided Paravertebral Catheter (PVB-A)- The Alaris pump will deliver 0.2% Ropivacaine at a rate of 10 ml/hr
2. Single Shot Paravertebral Block- placed by ultrasound using 0.2% Ropivacaine bolus.
3. Thoracic Epidural- The Alaris pump will deliver an epidural mixture of 0.125% bupiv/hydromorphone

Randomization will be stratified by prior opioid experience (opioid naïve or opioid tolerant). Separate randomization lists will be used for the two strata.

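### Randomization is stratified by opioid status, but no planned analysis uses the stratum; adding it costs almost nothing and gains precision if status predicts the outcome

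*Combined protocol and SAP*

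**What the plan says.** Section 3.0 sets the allocation: "A total of 120 subjects will be randomized by a computer program into three groups (40 per group"). It goes on: "Randomization will be stratified by prior opioid experience", with two levels, naive and tolerant, and "Separate randomization lists will be used for the two strata". It does not say whether the lists are blocked.

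Section 7.0 sets the analyses:

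- **Primary outcome (VAS at 24 and 48 hours).** "the model will include fixed effects for group, time, and the group by time interaction". The random effects cover only the correlation between the two times and their unequal variances.
- **Continuous secondary outcomes.** "Pain and satisfaction scores and opioid usage over time will be analyzed using repeated measures ANOVA". No covariate or stratum is named.
- **Ordinal secondary outcomes.** "Nausea and sedation scores will be compared between groups at each time point using Mantel-Haenszel chi-square tests for ordered categorical data". No stratifying variable is named, so the plan is silent on whether these tests are stratified.

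Opioid status does not enter any analysis as a covariate, stratum or subgroup.

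**The concern.** Opioid status is the only factor chosen for stratification, which suggests that the sponsor expects it to matter for pain or opioid use. If it does, a model without it leaves the variation between strata in the residual.

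The consequence depends on how the lists are built:

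- **Blocked lists.** The groups are balanced on status, so the true variability of a group difference is the within-stratum variability. The unadjusted model still reports the larger total variability. Its standard errors are then too large and its tests conservative.
- **Unblocked lists.** The unadjusted tests keep their nominal level, and only precision is lost.

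In both cases the group differences from the linear models are unbiased. What is at stake is interval width, power for differences smaller than the planning effect, and power for outcomes tied closely to tolerance, with opioid usage the obvious candidate.

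**Working it through.** **Inputs from the documents (Sections 3.0 and 7.0).** 40 per group, three groups; coefficient of variation 0.70; 60% decrease; two-sided 5% for each comparison.

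**Assumptions, because the documents give no figure.** Tolerant share p = 0.25 (range 0.10 to 0.40). Stratum difference d = 0, 0.5 or 1.0 within-stratum SD for VAS, and 1.0 to 1.5 for opioid usage. Block size 6 where lists are taken as blocked. The main calculation uses the raw scale with equal SDs, a single time point and a pairwise comparison.

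**Step 1. The plan's own claim.** It states that "the study will be able to detect a 60% decrease in VAS score between any two groups" but gives no power. In units of the reference mean, the SE of a pairwise difference is 0.70 × √(2/40) = 0.1565. The standardized effect is 0.60 / 0.1565 = 3.83. Power is 96.9% by the normal approximation and 96.6% to 96.7% by the noncentral t. The claim holds with room to spare; 80% power is reached at a decrease of about 44%.

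**Step 2. SE penalty from omitting the stratum.** Total variance is the within-stratum variance times 1 + p(1−p)d², so

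SE(unadjusted) / SE(adjusted) = √(1 + p(1−p)d²).

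At p = 0.25, p(1−p) = 0.1875:

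- d = 0.5: √(1 + 0.1875 × 0.25) = 1.023
- d = 1.0: √(1 + 0.1875) = 1.090
- d = 1.5: √(1 + 0.1875 × 2.25) = 1.192

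At d = 1.0 the ratio is √1.09 = 1.044 for p = 0.10 and √1.24 = 1.114 for p = 0.40.

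**Step 3. Type I error with blocked lists.** The unadjusted test rejects when |Z| exceeds 1.96 × ratio. The cut-offs 1.96, 2.005, 2.136 and 2.337 (d = 0, 0.5, 1.0 and 1.5) give 5.0%, 4.5%, 3.3% and 1.9%.

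**Step 4. Power and interval width.** The total SD is held at 0.70 and the SE divided by the ratio. The unadjusted half-width is 1.98 × 0.1565 = 0.31.

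| | Unadjusted | Adjusted, d = 0 | d = 0.5 | d = 1.0 |
|---|---|---|---|---|
| Power, 60% decrease | 96.7% | 96.7% | 97.3% | 98.5% |
| Power, 40% decrease | 72% | 72% | 74% | 79% |
| Decrease detectable with 80% power | 44% | 44% | 43% | 41% |
| 95% CI half-width (% of reference mean) | 31% | 31% | 30% | 28% |

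**Step 5. Simulation** (120 patients, three groups, p = 0.25, 20,000 runs per scenario). Type I error, unadjusted/adjusted:

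| d | Blocks of 6 | Unblocked |
|---|---|---|
| 0 | 4.9/4.9% | 5.1/5.1% |
| 0.5 | 4.3/4.7% | 4.9/4.9% |
| 1.0 | 3.0/4.9% | 5.0/4.8% |
| 1.5 | 1.9/4.8% | 5.2/5.0% |

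At d = 1.0, adjustment moves power at a 60% decrease from 97.8% to 98.5% (blocked) or 96.5% to 98.4% (unblocked). At a 40% decrease it moves from 73% to 79% or from 71% to 78%. A separate simulation with 30% tolerant, d = 1.0 and blocks of 6 gave type I error of 3.0% without the term and 4.9% with it.

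**Step 6. Nausea.** Assumptions: 50/25/17/8% over scores 0 to 3 in naive single-shot patients, and an odds ratio for tolerance of 1, 2 or 4. With blocked lists (10,000 runs), type I error unstratified/stratified is 5.2/5.3%, 4.7/5.1% and 3.5/4.8%. Power, with both catheter arms at an odds ratio of 3.5 against single shot, is 78/78%, 80/81% and 77/81%.

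**The case against.** The strongest reply is that nothing is broken. Type I error is not inflated, the linear-model differences are unbiased, and the plan already has about 97% power at its own effect size. With blocked lists the simulated gain there is only 0.7 points even at a 1.0 SD stratum difference. All of this stands.

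The non-zero figures also rest on assumptions about the tolerant share, the stratum effect and blocking. That stands too, and zero benefit is within the range shown. What is certain is the omission, not its size.

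The gain also depends on scale. Section 7.0 states variability as a coefficient of variation and allows a log transformation. At a 40% decrease with d = 1.0 (two-sample t, 78 df), power goes from 86% to 92% on the raw scale with constant CV, and from 95% to 97% on the log scale, against 71% to 79% with equal SDs. At 60% the gain on those two scales is essentially nil. On the log scale, a gain of about 8 points appears only near a 30% decrease (70% to 78%). This shrinks the benefit without removing it.

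The comparison of the two catheter arms lies outside the stated hypotheses, which set both against single shot; only the sample-size sentence covers every pair. The nausea gain is also small unless tolerance has a strong effect, and sedation was not simulated.

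Finally, a fixed effect does not carry over to the nonparametric tests that Section 7.0 allows as a fallback. That is correct, and the fix below covers it.

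**Conclusion.** The concern holds. Randomization is stratified by opioid status and no planned analysis names the stratum. The effect is modest and in the safe direction. With 25% tolerant and a VAS stratum difference of 0 to 1.0 SD, the unadjusted SE is 0% to 9% larger than it need be (4% to 11% at 1.0 SD with 10% to 40% tolerant). For opioid usage, if the stratum difference is 1.0 to 1.5 SD on the analysis scale, it is 9% to 19% larger, with type I error of 3.3% down to 1.9% if lists are blocked.

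The conclusion about the 60% decrease does not change. The gain lies in narrower intervals, smaller differences and outcomes tied to tolerance. Naming the term in advance also closes a modelling choice that would otherwise remain open once the data are seen. The change is recommended because it is nearly free, not because the current analysis is invalid.

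**What to change.** In Section 7.0:

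- Add opioid stratum (naive/tolerant, as used to select the randomization list) as a fixed effect in the primary VAS model and in the repeated measures models for pain, satisfaction and opioid usage.
- Run the nausea and sedation comparisons as Cochran-Mantel-Haenszel row-mean-score tests stratified by opioid status.
- Where a nonparametric test replaces a model, use a version stratified by opioid status, such as the van Elteren test for pairwise comparisons.

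It would also help to state in Section 3.0 whether the lists are blocked, since that decides whether the unadjusted tests would be conservative.

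The cost is a sentence or two of text and one degree of freedom per model. Status must already be known to choose the list, so no new data and no more patients are needed. If status turns out not to predict the outcome, the adjusted SE is only about 0.4% larger (simulated, unblocked lists).

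### The primary VAS model lets variance differ by time but not by arm; if the 0.70 coefficient of variation holds in each arm, raw-scale pairwise standard errors are off whenever arm means differ

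*Combined protocol and SAP*

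**What the plan says.** Section 7.0 makes VAS at 24 and 48 hours the primary outcome, analysed by repeated measures ANOVA. On the mean structure, "the model will include fixed effects for group, time, and the group by time interaction". On the covariance, it has "random effects to allow correlations between the two times and different variances for the two times". Variance by group is not mentioned, and the standard error for pairwise contrasts is not spelled out. A variance common to the arms is the natural reading, not explicit text.

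The sample-size paragraph of the same section gives spread only in relative terms: "the coefficient of variation for the VAS score at 24 and 48 hours is estimated to be 0.70". The effect is also relative: "With a sample size of 40 per group the study will be able to detect a 60% decrease in VAS score between any two groups". The sizing takes each test as two-sided at 5%. For the analysis, "A 5% significance level will be used for all comparisons".

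Section 7.0 also provides that distributions will be examined and that a transformation (the natural logarithm is the example) or nonparametric tests may be used where needed. It gives no criterion for switching and does not mention unequal spread between groups.

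**The concern.** The authors considered unequal variances explicitly and allowed for them in one of two dimensions. A CV used with a percent effect suggests that the SD falls with the mean. An arm with 60% less pain would then have an SD of 0.28 against 0.70 for single shot, in units of the single-shot mean. A variance averaged over three such arms fits no particular pair.

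The primary hypothesis sets two techniques each against single shot. One working and the other not is a realistic result. In that case the ineffective technique would be declared better too often, and a preceding overall group test would not protect, because the effective arm makes it significant.

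**Working it through.** **Inputs.** CV 0.70, 60% decrease and two-sided 5% per test (Section 7.0); 40 per arm (Sections 3.0 and 7.0). Assumptions not in the plan: the same CV in every arm; raw-scale analysis; pairwise standard errors from one variance common to the arms; and, for simulation only, a correlation of 0.5 between the two times.

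**The plan's own figure.** No power is stated, so the 60% has no unique reproduction. With a common SD of 0.70 x the reference mean, SE = 0.70 x sqrt(2/40) = 0.1565, 0.60/0.1565 = 3.83, and power = Phi(3.83 - 1.96) = 96.9%. The figure does not depend on the present point.

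**Step 1: arm SDs** (single-shot mean = 1). Means of 1, 0.7, 0.6 and 0.4 give SDs of 0.70, 0.49, 0.42 and 0.28.

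**Step 2: formulas.** Model SE = sqrt(2V/40), with V the mean of the three arm variances. True SE = sqrt((SDi^2 + SDj^2)/40). With r = model SE / true SE, coverage of a nominal 95% interval = 2 Phi(1.96 r) - 1. If the correlation is the same in every arm, averaging the two times scales all SEs alike and leaves r unchanged.

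**Step 3: one technique works, one does not** (means 1, 1, 0.4). V = (0.49 + 0.49 + 0.0784)/3 = 0.3528. Model SE = sqrt(0.7056/40) = 0.1328. True SE for the two equal arms = sqrt(0.98/40) = 0.1565. So r = 0.849, coverage is 90.4% and type I error is 9.6%.

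**Step 4: both work** (means 1, 0.4, 0.4). V = (0.49 + 0.0784 + 0.0784)/3 = 0.2156 and model SE = sqrt(0.4312/40) = 0.1038. Against single shot, true SE = sqrt(0.5684/40) = 0.1192, r = 0.871, coverage 91.2%. Epidural versus catheter: true SE = sqrt(0.1568/40) = 0.0626, r = 1.658, coverage 99.9%.

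| Means | Pair | r | Coverage |
|---|---|---|---|
| 1, 1, 0.4 | two equal high-mean arms | 0.849 | 90.4% |
| 1, 1, 0.7 | two equal high-mean arms | 0.911 | 92.6% |
| 1, 0.4, 0.4 | single shot vs either | 0.871 | 91.2% |
| 1, 0.4, 0.4 | epidural vs catheter | 1.658 | 99.9% |
| 1, 0.7, 0.7 | single shot vs either | 0.941 | 93.5% |
| 1, 0.7, 0.7 | epidural vs catheter | 1.161 | 97.7% |
| 1, 1, 1 | any | 1.000 | 95.0% |

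**Step 5: simulation** (gamma VAS, CV 0.70, contrasts of the 24/48-hour average, several sets of 2,500 to 6,000 runs; ranges are across sets).
- Ineffective technique vs single shot, the other technique 60%, 40% or 30% lower: type I error 9.4-10.2%, 7.8-8.9% and 7.2-7.9% with the common variance. With arm-specific variances, null comparisons stayed at 4.4-5.8%.
- Both lower: coverage against single shot about 90-93%.
- Epidural = catheter, both 60% lower: rejection 0.2-0.5% instead of 5%.
- Catheter a further 30% below epidural: power with the common variance 16-17% at an epidural mean of 0.4, 43-45% at 0.6 and 54% at 0.7. With arm-specific variances it was 72-74% (checked at 0.4 and 0.6).
- Power against single shot when both are 60%, 40% or 30% lower, common vs arm-specific: 100% vs 100%, 97% vs 96%, and 78% vs 74%.
- All arms equal: about 5% either way.

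**The case against.** The strongest reply is that Section 7.0 already names the remedy. A constant CV is the standard case for a log transformation, which equalises spread across arms. On the log scale, keeping the common variance, the simulated type I error returns to 4.8-5.4% when there are no zeros. This largely stands. What it leaves open is that the switch is conditional, has no trigger, does not mention unequal group variances, and cannot take a VAS of 0 without an offset. With log(VAS + 1) on an assumed 0-10 scale, the level ranged from 3.4% to 7.4% depending on the set-up. The documents give no proportion of zeros.

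A reader might infer that the nonparametric fallback would fail too. The material does not support that for the type I errors above: the two arms being compared have identical distributions, and a pairwise rank test kept its level (5.2-5.6%).

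A reader might also infer that the plan's CV proves the SDs differ by arm, so that the intervals are simply wrong. It does not. The plan gives a single planning value from earlier studies and names no arm. A CV may just express an SD relative to a reference mean, and on a bounded scale the SD need not follow the mean.

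Finally, the largest distortions concern epidural versus catheter. That contrast is outside the stated primary hypothesis, although the sizing sentence covers any two groups. Rejecting too rarely when those arms are equal is conservative rather than a false claim; the cost is lost power when they differ.

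**Conclusion.** The point holds conditionally. The default raw-scale model frees variance by time only. If the CV is about constant across arms and the arm means differ, its pairwise standard errors err in both directions. Type I error is about 7-10% for an ineffective technique when the other is 30-60% lower, coverage against single shot is about 90-93% when both are lower, and epidural versus catheter becomes very conservative.

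There is no distortion when all arms are equal, and power for the primary contrasts barely moves when both techniques work. The result rests on the constant CV, raw-scale analysis, a pooled pairwise standard error and, for the simulated figures, a correlation of 0.5. It is a worthwhile low-cost improvement. It is not a must-fix, because the premise is inferred and the optional log would remove most of the effect.

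**What to change.** In Section 7.0, state that the primary VAS model estimates an unstructured 2x2 covariance for the two times separately in each arm, with Kenward-Roger or Satterthwaite degrees of freedom, and that all pairwise contrasts and 95% intervals come from it. In SAS PROC MIXED this is REPEATED time / SUBJECT=id TYPE=UN GROUP=arm, with DDFM=KR or DDFM=SATTERTHWAITE on the MODEL statement. The plan allows SAS or SPSS, so the package chosen must be able to fit it.

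If the transformation clause is kept, add a criterion for using it and a rule for a VAS of 0. A prespecified log-scale primary analysis with a zero rule, or robust standard errors, would also be acceptable. The arm-specific covariance is preferred because it keeps the VAS scale, accepts zeros and removes a choice made after seeing the data.

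The cost is a sentence and a program option. The model has 9 covariance parameters instead of 3 (3 per arm x 3 arms), so a few degrees of freedom are lost if the variances turn out equal. With 40 per arm that is negligible: the level stayed near 5% with all arms equal.

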Previous studies have demonstrated that both thoracic epidurals and paravertebral blocks provide adequate analgesia for VATS. Thoracic epidurals provide excellent pain relief but are associated with hypotension and more nausea/vomiting. Paravertebral catheters have the advantage of having a lower side effect profile than thoracic epidurals. Paravertebral blocks have also been shown to improve respiratory function after surgery. Single shot paravertebral blocks have been described as providing adequate post-VATS pain control, despite a shorter duration of action compared to catheter. In order to evaluate the effectiveness and the side effects of the different pain modalities for post-VATS pain control, we will compare these three different methods of pain blocks:

- 1)single shot paravertebral block
- 2)paravertebral catheters
- 3)thoracic epidural

Rationale and Specific Aims

All of the pain control modalities allow for titration and continuous infusion of local anesthetic to achieve adequate pain control for the duration that the catheter remains in place, except for the single shot paravertebral block. The specific aim of the study is to compare the difference between the three pain blocks in achieving the following:

1. Improved postoperative pain scores
2. Decreased opioid requirements
3. Improved patient satisfaction scores
4. Decreased opioid side effects (Nausea, sedation, ileus, urinary retention, respiratory depression)

The primary endpoint of this study will be VAS pain score. The VAS scores will be taken with both rest and movement.

The secondary endpoint includes intravenous opioid consumption and opioid side effects (nausea, sedation, ileus, urinary retention, respiratory depression). The IV and PO opioid doses will be quantified at 1, 24, 48, and 72 hours. We will also measure postoperative nausea and sedation scores at 1, 24, 48, and 72 hours. We will also measure time to first bowel movement, incidence of urinary retention, incidence of respiratory depression, and time to discharge. If subjects are discharged prior to completing the 72-hour endpoints, efforts will be made to contact them and obtain data points. If unable to be reached, or unable to collect data, we will not consider these deviations since it will not change the integrity of the study data.

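### The Mantel-Haenszel test for nausea and sedation is under-specified: run once across three unordered arms, its p-value depends on the arm codes

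*Combined protocol and SAP*

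**What the plan says.** Section 4.0 scores nausea and sedation on ordered 0-3 scales at 1, 24, 48 and 72 hours. Section 7.0 gives the analysis: "Nausea and sedation scores will be compared between groups at each time point using Mantel-Haenszel chi-square tests for ordered categorical data". It names SAS or SPSS as the software and a 5% level for every comparison. It gives no degrees of freedom and no scores for the arms. It does not say whether there is one three-arm test or a set of two-arm tests.

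The secondary hypothesis in Section 7.0 is that epidural and paravertebral catheter will both show "decreased nausea and sedation scores compared to single shot paravertebral".

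The arms are listed in more than one order. The randomization list in Section 3.0 puts the catheter first, then "Single Shot Paravertebral Block- placed by ultrasound", then epidural. The list in Section 1.0 opens with "1)single shot paravertebral block", followed by catheter and epidural. No section assigns analysis codes.

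Section 3.0 stratifies randomization by prior opioid experience: "Separate randomization lists will be used for the two strata". Section 7.0 does not carry the strata into this test.

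**The concern.** The usual Mantel-Haenszel chi-square for ordered categories is a correlation test. It needs a number for each arm as well as for each score, and it looks only for a straight-line trend across those numbers. That suits a dose series, but these arms are three different techniques.

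The plan's hypothesis is that two arms are better than the third. If the third arm carries the middle code, as in the Section 3.0 list, a trend test is looking in the wrong direction. Other codes give a different p-value from the same data. With two scores at four times, eight tests are exposed. A null result could be reported as no difference in side effects, although comparing side effects across the techniques is part of the study's declared aim.

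**Working it through.** **Plan's own figure.** There is none to reproduce. The only sample-size statement in Section 7.0 concerns VAS.

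**Inputs from the documents.** Three arms of 40, N = 120 (Section 3.0); scores 0-3 (Section 4.0); level 5% (Section 7.0); arm orders from Sections 3.0 and 1.0.

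**Assumed inputs.** The documents give no nausea or sedation distributions. Three single-shot distributions over scores 0/1/2/3 were used: A = 35/30/20/15%, B = 50/25/15/10%, C = 70/15/10/5%. In the other arms the odds of a worse score are divided by an odds ratio (OR) at each cut-point.

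**Step 1: what the statistic measures.** With codes 1, 2, 3 and 40 per arm, the code deviations are -1, 0, +1. Their sum of squares is 40 × 2 = 80, and the cross-product with the scores is 40(m3 - m1), where m1 and m3 are the mean scores of the arms coded 1 and 3. So

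Q = (N-1)r² = 119 × [40(m3 - m1)]² / (80 × T) = 2380 (m3 - m1)² / T,

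where T is the total sum of squares of the scores. The mean of the arm coded 2 enters only through T.

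**Step 2: apply the two orders.**
- Section 3.0 order: m3 - m1 is epidural minus catheter. Single shot has zero weight. If both arms benefit equally, the difference is zero whatever the score distribution.
- Section 1.0 order: m3 - m1 is epidural minus single shot. The catheter now has zero weight.
- The hypothesis in Section 7.0 names epidural, catheter, then single shot. That reverses the Section 1.0 order and gives the same r².

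**Step 3: one case by hand (distribution A, OR 3 in both arms).** The single-shot mean is 0.65 + 0.35 + 0.15 = 1.15. Dividing the three cumulative odds by 3 gives probabilities of 0.382, 0.152 and 0.056, so the mean is 0.59. The variances are 1.128 and 0.768. The within-arm sum of squares is 40 × (1.128 + 2 × 0.768) = 106.6. The between-arm sum is 40 × (2/3) × 0.56² = 8.36. T is about 115.
- Section 3.0 order: 2380 × 0² / 115 = 0.
- Section 1.0 order: 2380 × 0.56² / 115 = 6.5, which is about 72% power on 1 df.
- 2-df row-mean-scores test: 119 × 8.36 / 115 = 8.7, about 75% power.

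**Step 4: simulation, 20,000 trials per case.** Rejection rates (%) for A / B / C:

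| OR catheter, epidural | 1 df, Section 3.0 order | 1 df, Section 1.0 order | 2 df row mean scores |
|---|---|---|---|
| 1, 1 (null) | 4.8 / 4.9 / 5.0 | 5.0 / 5.2 / 4.9 | 4.9 / 4.9 / 4.6 |
| 3, 3 | 2.8 / 2.4 / 1.7 | 73.1 / 66.0 / 49.6 | 74.8 / 66.9 / 47.9 |
| 4, 2 | 24.3 / 16.7 / 8.9 | 40.1 / 37.0 / 29.4 | 79.6 / 69.9 / 48.7 |
| 2, 0.5 | 91.1 / 89.0 / 77.6 | 39.8 / 41.1 / 37.1 | 84.9 / 81.7 / 67.7 |

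Pairwise 1-df tests against single shot at OR 3 have 45-71% power, and coding does not affect them. Repeat runs moved the ends of the ranges by about one point; the verdict uses the widest ends.

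The 1-df rate in row 2 falls below 5% because the single-shot difference inflates T without adding to the numerator. In row 4 epidural is worse than single shot, so the stated hypothesis is false, yet the overall tests reject often. A significant overall result therefore does not establish the hypothesis; pairwise results are needed.

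**The case against.** A reader might infer that the plan commits itself to a test blind to its own hypothesis. The documents do not support that, for four reasons.

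- **Other tests fit the sentence.** The word ordered may describe the 0-3 scores alone. Pairwise tests would match a hypothesis framed against single shot; with two arms, 1 df is correct and coding is irrelevant. The mean-score test belongs to the same Mantel-Haenszel family. This stands, and it limits confidence. But the plan states neither option, and the same paragraph uses similar between-groups wording for the primary three-arm model.
- **There is no single protocol order.** Section 1.0 puts single shot first, and equal benefit then costs the 1-df test nothing material. This stands too, although it also shows that the result turns on an arbitrary choice.
- **Zero trend needs equal benefit.** Section 7.0 says both arms are better, not equally so, and Section 1.0 associates epidurals with more nausea and vomiting. With unequal benefit, power in the Section 3.0 order is low but not nil.
- **The magnitudes rest on assumed distributions.** This is true of every power figure. It is not true of the zero weight in Step 2, which is algebra.

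Leaving out the strata is a plan-wide gap, since Section 7.0 uses them in no analysis. No size is claimed for it here.

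**Conclusion.** The concern holds as a conditional one. Section 7.0 names a statistic whose usual form is unsuited to three nominal arms, and it does not say how the arms enter. If that statistic is run once across the arms, the p-value depends on arbitrary codes.

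- **Equal benefit (OR 3 in both arms).** Section 3.0 numbering gives about 2-3% power, against 47-76% for the 2-df test. In the Section 1.0 order the 1-df test does about as well as the 2-df test.
- **Unequal benefit (OR 4 and 2).** Power is 9-25% in Section 3.0 order and 29-40% in Section 1.0 order, against 48-80%.

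These figures assume 40 evaluable patients per arm, the three distributions above and proportional odds. Type I error is about 5% under any coding. Only secondary outcomes are affected. The change should be made, with medium confidence that the plan would otherwise be run in the harmful way.

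**What to change.** Replace the sentence in Section 7.0 with:

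> Nausea and sedation scores at each time point will be compared with the Cochran-Mantel-Haenszel row-mean-scores-differ test (2 df, arm nominal, score ordinal), stratified by opioid-naive/tolerant status, followed by pairwise comparisons of paravertebral catheter and of epidural, each with single shot, when the overall test is significant.

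This costs one sentence and no new data. It means eight overall tests and at most 16 pairwise ones (2 scores × 4 times × 2 comparisons). The gate limits pairwise testing within each score and time point; it does not adjust across the eight, and the plan should say so.

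The downside is a little power lost to a 1-df test if the arms happened to be coded in the order of the true effect: 68-85% against 78-91% in the last row of the table.
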